## 5.1. Potential Risks

**5.1.1. Emotional discomfort during self-report measures and interviews.** Participants could develop mild to moderate emotional discomfort or frustration associated with filling out questionnaires and/or answering interview questions that ask about traumatic or stressful experiences, psychological symptoms, and thoughts about suicide. This potential risk is expected to be comparable to the discomfort experienced when talking with a friend or acquaintance about these same topics. If discomfort is experienced, it is not expected to be severe or to last for more than a few minutes.

**5.1.2. Emotional discomfort during treatment.** Some participants may experience increased emotional distress (e.g., anxiety, guilt, shame) during the course of treatment, especially when asked to talk about traumatic or stressful experiences. This could lead to an increase in sleep disturbance, nightmares, or intrusive memories. This potential risk typically does not exceed the amount of discomfort experienced when thinking about these same topics, however, and typically does not last for more than a few hours. This risk is common among individuals with PTSD who receive CPT and other forms of mental health treatment, however, and is not related to the research itself.

**5.1.3. Breach of confidentiality.** Participants' confidentiality could be breached if their identifiers are inadvertently released or accessed by a third party. Participants could also be identified based on the content of their responses. This risk is expected to be low because the data are not stored or analyzed in ways that are likely to reveal a subject's identity. Breach of confidentiality could also occur if an external party or individual hacks into the Zoom interface during a participant's therapy sessions.

## 5.2. Protections Against Risk

To minimize the risk of emotional discomfort associated with survey questions and interviews, we will fully describe to participants the nature of study procedures and the potential for distress will be fully described to participants before they complete any procedures. Moreover, participants will be reminded that they can choose to discontinue any task at any time if they become severely distressed or stop the task and take a break. Research staff are instructed to closely monitor participants while they are completing the tasks.

Because we will be recruiting participants with a history of suicidal thoughts and behaviors, we expect some subjects to be experiencing elevated emotional distress. To minimize risk associated with this issue, all participants will receive either a safety plan during their first session, consistent with standard of care recommendations for the management of suicide risk. The investigators will also be available to meet with distressed participants for additional crisis interventions, where needed.

To minimize the risk of confidentiality breach, research staff will receive rigorous training in confidentiality and privacy procedures. Participant identifiers will also be stored separate from their data. Participant data will be tracked using a sequential numeric ID system generated for each subject (e.g., 1001, 1002, 1003...), and will be stored in a deidentified manner using participant IDs instead of potential identifiers. Finally, we will use recommended security procedures and strategies for maximizing confidentiality and minimizing the risk of third-party intrusion during Zoom-based research activities.

### **High-Risk Management Procedures**

The PI has independently conducted multiple studies with acutely suicidal individuals, and has considerable experience managing suicide risk. If a participant reports suicide ideation, or a research staff member becomes aware that the subject is at imminent risk to harm himself/herself, the following questions will be asked to clarify the nature of risk (and to identify those at imminent risk requiring consideration for hospitalization): (1) Do you have a plan for killing yourself and do you intend to act on the plan?; (2) Do you have a desire to kill yourself that you believe you might act on?; (3) Have you already taken steps to act on your plan? If so, what steps have you taken? It is also possible for subjects to be identified as imminent risk if they indicate a moderate to severe level of suicide intent on the Beck Scale for Suicide Ideation, requiring evaluation for possible hospitalization. Once a participant is identified as having potentially imminent risk, the researcher will conduct a more thorough assessment to include possible evaluation by a member of the research team, all of whom are clinical mental health providers, for possible hospitalization and/or notification of emergency services for the purposes of a rescue.

All participants will complete either a safety plan or a crisis response plan during their first appointment. The safety plan is a recommended strategy for reducing suicide risk that includes contact information for professional resources and crisis services within the participant's local community, as well as the National Suicide Prevention Lifeline phone number.

Finally, if a subject reports severe suicide ideation during an EMA response, an automated email alert will be sent to the research team via email and text message. Severe suicide ideation is defined as a score of 2 on the active suicide ideation item of the SSI, indicating a moderate to strong desire to make a suicide attempt. When an automated alert is received by the research team, a member of the research team will contact the subject to conduct a risk assessment to clarify the nature of risk using the same procedures outlined above, review the subject's safety plan, and determine if the subject is at imminent risk to harm himself/herself, thereby warranting further evaluation for possible hospitalization and/or activation of emergency services (e.g., wellness check by law enforcement). The participant's assigned clinician will also be notified so that suicide risk can be addressed during the next scheduled appointment, which will occur within 24 hours owing to the scheduling of therapy sessions on a daily basis.

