#### **3.5. Treatment Conditions**

Participants will be randomized to receive cognitive processing therapy (CPT) for PTSD with or without a crisis response plan (CRP). Both treatments will be scheduled on a daily basis during a 14-day window, and will be provided either in-person or via telehealth format, depending on the geographic location and preference of the participant.

In the **standard CPT** condition, participants will complete a self-guided safety plan, a procedure that includes personal warning signs for a suicidal crisis, self-management strategies, sources of social support, and contact information for professional resources and crisis services within the participant's local community, as well as the National Suicide Prevention Lifeline phone number. As a recommended standard care practice with suicidal patients, the combination of CPT and safety plan represents treatment as usual. The safety plan will be administered during the first therapy session.

In the **enhanced CPT** condition, participants will complete a CRP instead of a safety plan. The CRP is another recommended standard care practice with suicidal patients that includes many of the same elements as the safety plan (i.e., warning signs, self-management strategies, sources of social support, crisis services), but is created collaboratively by the patient with active input of their clinician rather than being self-guided. The CRP also includes a section focused on the participant's reasons for living, an

addition that has been shown to increase positive emotional states (e.g., hope, optimism) and lead to faster reductions in suicidal intent. The CRP will be administered during the first therapy.

The present study is therefore designed to examine if treatment effects on suicide ideation are improved with the addition of (a) active collaboration between a patient and clinician and (b) components that increase positive emotional states.

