## 4.3. Ecological Momentary Assessment

EMA assessments will be programmed and collected using MetricWire, a HIPAA-compliant EMA program that can coordinate sending mass text and email queries within a predetermined time-window. MetricWire collects de-identified responses using subject ID numbers. The program pushes assessment notifications to each subject's smartphone. Subject responses are then submitted to an encrypted server. MetricWire can automatically respond to invalid responses (e.g., numeric values outside the range of possible responses), filter multiple responses, and send standardized information to subjects based on predetermined response criteria (e.g., sending crisis hotline information for subjects indicating severe suicide ideation). Subjects will receive 4 EMA prompts per day on the 14 consecutive days coinciding with active treatment. EMA prompts will be sent at randomly selected times between 8 AM and 11 PM. EMA prompts will assess mood state, suicide ideation, PTSD symptom severity, emotion regulation strategies, location, and social context.

**4.3.1. Mood state** will be measured using a short form of the Positive and Negative Affect Scale (PANAS), a self-report scale that assesses positive and negative emotional states. Respondents are directed to rate the extent to which they are currently experiencing positive emotions and negative emotions.

**4.3.2. Suicide ideation** will be assessed using the first 5 items of the Scale for Suicide Ideation (SSI), described above in Section 4.1.1. The first 5 items assess intensity of the wish to live, wish to die, balance of the wish to live and wish to die, active suicide ideation, and passive suicide ideation.

**4.3.3. PTSD symptom severity** will be assessed using the NSESS, described above in Section 4.2.1.

**4.3.4. Location** will be assessed with a checklist that directs subjects to indicate their current location: home, work, school, friend's residence, family member's residence, bar/tavern/pub, indoor public space (e.g., grocery store, shopping center, gym), or outdoor public space (e.g., park, swimming pool). These items were selected to assess subjects' physical location.

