## 5. Detailed Study Procedures

The flow of participants through the study procedures are displayed in the figure below:

Potential participants will be recruited via a combination of methods outlined above in Section 3.2.1 and will complete an initial self-report screening to assess for the presence and intensity of psychological symptoms associated with PTSD and other common comorbid conditions (e.g., depression, panic disorder), and presence and intensity of suicide ideation. Potential participants will also be asked about their military service history. The entire screening process is expected to take less than 30 minutes to complete. Based on their responses to survey items, potential participants may be invited to share their contact information, which will be emailed to a member of the research team.

A researcher will then contact the potential participant to complete an eligibility interview conducted by phone or Zoom. During this interview, clinician-administered interviews will be completed to confirm the potential participant's primary diagnosis, to assess level of suicide risk (i.e., determining if there is imminent risk warranting immediate intervention and assistance), and to confirm prior military service. Individuals meeting eligibility criteria will then be given additional information about the study procedures and will be able to ask any questions about the study's procedures. The eligibility interview is expected to take approximately 1 hour to complete.

Those agreeing to continue their participation will be assisted in downloading the EMA data collection app to their smartphone, and will receive instructions on how to use the app. Finally, they will be

randomized to one of the two treatment groups and scheduled for their first therapy session. Participants will participate in one hour of psychological treatment per day for 12 consecutive business days (i.e., excluding weekends), for a total time commitment of 12 hours. They will also complete EMA surveys every day for 14 consecutive days (i.e., including weekends). EMA assessments will require 20 minutes per day, for a total of approximately 4.5 hours.

After completing treatment, participants will be given instructions on how to remove the EMA data collection app from their smartphones. Participants will be contacted 6 and 12 months postbaseline to complete the scheduled follow-up assessments. Each follow-up assessment is expected to take approximately 15 minutes to complete.

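### Twelve business-day sessions cannot fit the 14-day treatment window, and on that schedule the 24-hour session assurance after a severe-ideation alert fails from Friday's session until the same hour on Sunday

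*Combined protocol and SAP*

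**What the plan says.** Section 3.5 of the combined protocol and SAP gives the treatment calendar: "Both treatments will be scheduled on a daily basis during a 14-day window". Section 4.3 places four EMA prompts a day, at random times from 8 AM to 11 PM, on the "14 consecutive days coinciding with active treatment".

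Section 5 gives a different calendar. Participants receive "one hour of psychological treatment per day for 12 consecutive business days (i.e., excluding weekends", a total of 12 hours. The same paragraph says that EMA runs for 14 days in a row with weekends counted, so the distinction between the two calendars is deliberate.

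The High-Risk Management Procedures, under Section 5.2, describe what follows a score of 2 on the active-ideation item in an EMA response. An automated alert goes to the team, and "a member of the research team will contact the subject to conduct a risk assessment to clarify the nature of risk". A further step then follows: "The participant's assigned clinician will also be notified so that suicide risk can be addressed during the next scheduled appointment". That appointment is described as one "which will occur within 24 hours owing to the scheduling of therapy sessions on a daily basis".

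No section provides for weekend sessions or makes a weekend exception to the 24-hour statement.

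**The concern.** The 24-hour statement gives daily sessions as its reason. Section 5 says that sessions are not held on weekends, while EMA prompts, and so alerts, continue through them. The statement and the schedule cannot both hold.

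The issue is the accuracy of a safety procedure. The trigger is a severe level of suicide ideation. Staff or an ethics board reading the procedure would conclude that every alert is followed by a session with the participant's own clinician within a day. It is also the only step in the alert procedure that carries a stated number of hours, since the team's contact is tied to receipt of the alert without a figure. No bias in the H1 or H2 analyses is claimed.

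**Working it through.** **Inputs.** 12 sessions on business days (Section 5); a 14-day daily window (Section 3.5); 4 prompts a day for 14 days, so 4 × 14 = 56 prompts, sent between 08:00 and 23:00, a 15-hour day (Section 4.3); the 24-hour statement (High-Risk Management Procedures). Assumed, because the protocol does not say: sessions keep one clock time *h*, EMA starts with session 1, prompts are spread evenly over the 15 hours, and there are no public holidays.

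**1. The plan's own figure.** With sessions on all seven days, consecutive sessions are 24 hours apart. Twelve sessions span 12 days, which fits in 14, and any alert before the last session waits at most 24 hours. The 24-hour figure is therefore reproduced under Section 3.5 read literally, up to the last session.

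**2. Fit of the Section 5 schedule.** Any 14 consecutive days contain exactly 10 business days, so 12 − 10 = 2 sessions fall outside. Counting EMA days from session 1, session 11 is on day 15 for every weekday start. Session 12 is on day 16 for a Monday to Thursday start and on day 18 for a Friday start. EMA then ends before sessions 11 and 12.

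**3. Alerts with no session within 24 hours.** The Friday-to-Monday gap is 72 hours. An alert waits more than 24 hours if it comes after Friday's session and before hour *h* on Sunday. The prompt hours in that interval are:

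- Friday: 23 − *h*
- Saturday: 15
- Sunday: *h* − 8
- Sum: (23 − *h*) + 15 + (*h* − 8) = 30 hours, whatever *h* is

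That is 30/15 × 4 = 8 prompts per weekend. Fourteen days contain two such weekends, so 16 of 56 prompts (28.6%). The remaining 56 − 16 = 40 (71%) have a session within 24 hours.

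**4. Length of the wait.** The maximum is about 72 hours, just after Friday's session. The mean wait of the 16 prompts at three assumed session hours is below; each cell gives prompt hours and the mean wait from them to Monday's session.

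| Session hour | Friday | Saturday | Sunday | Mean wait |
|---|---|---|---|---|
| 09:00 | 14 h, 65 h | 15 h, 41.5 h | 1 h, 24.5 h | (910 + 622.5 + 24.5)/30 = 51.9 h |
| 13:00 | 10 h, 67 h | 15 h, 45.5 h | 5 h, 26.5 h | (670 + 682.5 + 132.5)/30 = 49.5 h |
| 17:00 | 6 h, 69 h | 15 h, 49.5 h | 9 h, 28.5 h | (414 + 742.5 + 256.5)/30 = 47.1 h |

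**5. Start of EMA.** The assessment table also marks EMA in the pre-treatment column. An earlier EMA start does not lower the count in step 3, because any 14 consecutive days contain two Fridays, two Saturdays and two Sundays.

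**The case against.** The strongest reply is that little depends on the sentence. The session is an additional step. The main response is the alert itself, followed by contact, risk assessment, review of the safety plan and, if needed, emergency services. The High-Risk Management Procedures describe the members of the research team as clinical mental health providers, so a weekend alert already leads to assessment by a clinician. Section 5.2 adds that "The investigators will also be available to meet with distressed participants for additional crisis interventions, where needed". Section 4.3 mentions "sending crisis hotline information for subjects indicating severe suicide ideation", though as something the software can do. Every participant also has a safety plan or crisis response plan from the first session. All of this stands. A reader might infer that a participant with severe ideation is left without a response over the weekend; the documents do not support that.

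A second reply is that Section 5 is the outlier. The 14-day window in Section 3.5, the 2-week assessment in Section 3.8 and the treatment column for weeks 1-2 in the assessment table agree with one another, and the 24-hour sentence is consistent with Section 3.5. A drafting slip in Section 5 is plausible. But Section 5 is the most explicit of these passages, and it sets weekend-free sessions beside weekend-inclusive EMA in so many words. The conflict has to be resolved by the sponsor, not by the reader.

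A third reply is that the failure is not general. That is correct. Sunday alerts later than Monday's session hour do have a session within 24 hours. Of Saturday and Sunday prompts taken alone, the share that fails is 16/30 = 53% with 09:00 sessions and 24/30 = 80% with 17:00 sessions, not all of them.

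A reader might also infer that the assurance is wrong under any schedule, because 12 daily sessions from EMA day 1 end on day 12 and EMA runs to day 14. Those late prompts have no next appointment at all, and the sentence presupposes one. That is a gap to close in the wording, secondary to the conflict between Sections 3.5 and 5.

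**Conclusion.** The point holds as an internal inconsistency that makes one statement in a suicide-risk procedure untrue on the protocol's own schedule. Twelve business-day sessions need 16 or 18 calendar days and cannot fit the 14-day window. If Section 5 governs, the 24-hour statement fails for 16 of 56 scheduled prompts (29%), with a longest wait of about 72 hours.

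The count does not depend on the weekday of the first session or on the session hour, provided the hour is constant and lies within the prompt window. It assumes that EMA starts with session 1. It is a share of scheduled prompts, not of alerts: the documents give no alert rate, and Section 6 expects up to 50% of EMA data to be missing.

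The consequence is limited. What is misstated is how soon the participant's own clinician follows up. The alert-triggered contact and risk assessment do not depend on session days and are neither removed nor delayed.

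**What to change.** State one session schedule in Sections 3.5, 4.3 and 5.

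- If business days govern, change the treatment window to 16-18 days, or cut the course to 10 sessions. Replace the 24-hour clause with wording to the effect that the clinician follows up at the next scheduled session, which may be up to about 72 hours later over a weekend.
- If sessions on all seven days are intended, remove the weekend exclusion from Section 5. The 24-hour clause can then stay for alerts before the last session.

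Under either choice, state that the research team's contact on receipt of an alert applies on weekends and after the final session for as long as EMA continues. Any time limit on that contact should be set by the clinical team and be no looser than the present contact on receipt; a 24-hour ceiling, for example, could be read as a relaxation.

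The cost is protocol wording and explicit weekend cover for a contact that the protocol already requires. EMA length, sample size and the planned analyses do not change.

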## **6. Data Analysis**

Prior to statistical analyses, we will visually inspect data to ascertain distributional properties and determine if data meet the assumptions for each of our planned analyses. Based on our previous studies, we expect the primary outcome (suicide ideation) to be positively skewed. If true for this study, we will consider and evaluate the most appropriate method for approaching each analysis (e.g., data transformations, bootstrapped confidence intervals, use of generalized linear modeling). We anticipate having up to 50% missing data from EMA and up to 30% missing data from follow-up. We will first use Little's test to determine if the missing data are ignorable (i.e., missing completely at random or missing at random). If the missing data are not ignorable, we will use multiple imputation. The number of imputed datasets will be determined based on the percent of data that are missing and contemporary recommendations. Our primary outcome for Aim 1 is suicide ideation, measured using the SSI total score.

For H1, we will use generalized linear mixed models with SSI total score as the outcome variable and treatment, time, and treatment x time entered as predictors. We will first assess change in SSI scores across the four primary time points: baseline, posttreatment, 6 months, and 12 months. H1 will be supported if there is a statistically significant treatment x time interaction indicating a faster reduction in suicide ideation among participants receiving CPT+CRP. Sensitivity analyses will then be conducted with SSI total scores from the initial screening and the eligibility interview added to the model, thereby enabling us to determine if reductions in suicide ideation coincided with the start of treatment and ruling out the possibility that observed differences between groups is attributable to pre-treatment temporal trends (e.g., participants in one group showing reductions in suicide ideation that precede the initiation of treatment).

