### **3.8. Sample Size Estimation**

The primary outcome, suicide ideation, will be assessed up to 4 times: baseline, 2 weeks, 26 weeks, and 52 weeks). We will analyze data from the full sample and also conduct separate analyses for two subgroups of interest: those with suicide ideation at baseline and those without suicide ideation at baseline. Our primary planned analyses entail slope comparisons for suicide ideation scores.

Our assumptions for sample size estimation were based on previous research conducted by our team. In two separate pilot studies of our two-week treatment program, 50-70% of participants reported suicide ideation at baseline. We used this range to estimate the percentage of participants expected to report suicide ideation at baseline. We also based estimates on the results of a published RCT comparing the CRP to treatment as usual (Bryan et al., 2017a), which found small to moderate differences in suicide ideation between treatment groups over time ( $0.3 < d < 0.7$ ). We used this range to estimate a lower bound for the anticipated effect size (i.e.,  $d=0.3$ ).

Assuming a two-tailed  $\alpha < .05$ , a within-between interaction (i.e., treatment x time), a small correlation ( $r=0.1$ ) among repeated measures, a sample size of 112 ( $n=66$  per group) provides 80% power to detect an effect size equivalent to  $d=0.3$ . To account for expected attrition (~25%) and missing data (participants completing only 3 of 4 scheduled assessments), we will aim to enroll a total of  $N=150$  ( $n=75$  per arm) eligible participants, which provides 86% power to detect an effect size equivalent to  $d=0.3$ . Assuming two-thirds of the sample report suicide ideation at baseline—a rate comparable to our pilot studies—we will have 80% power to detect a minimum effect size of  $d=0.38$  among participants endorsing suicide ideation at baseline. Because we expect to consent and screen approximately 5 veterans to identify each eligible participant who consents to treatment, we will therefore enroll a total of 750.

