### **4.1. Primary Outcomes**

**4.1.1. Suicide ideation** will be measured using the Scale for Suicide Ideation (SSI), an empirically-supported self-report scale that assesses the intensity of suicide-related thoughts, urges, intentions, and behaviors. All subjects complete the first 5 items. If a subject positively endorses either item 4 (active ideation) or item 5 (passive ideation), they are directed to complete an additional 14 items.

**4.1.2. Suicidal behaviors** will be measured using the Self-Injurious Thoughts and Behaviors Interview-Revised (SITBI-R), an empirically-supported self-report scale that assesses a range of self-injurious behaviors including suicide attempts, interrupted suicide attempts, preparatory behaviors, and non-suicidal self-injury.

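### Little's test cannot show that missing SSI data are ignorable, the fallback imputation itself assumes MAR, and no analysis examines data missing not at random

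*Combined protocol and SAP*

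**What the plan says.** All the missing-data text for the analysis is in section 6 (Data Analysis). The scale of the problem is stated: "We anticipate having up to 50% missing data from EMA and up to 30% missing data from follow-up". Little's test is then used "to determine if the missing data are ignorable (i.e., missing completely at random or missing at random". The consequence follows: "If the missing data are not ignorable, we will use multiple imputation". On the imputation, the plan adds only that the number of datasets will follow from the percentage missing and current recommendations. It names no imputation model, variables or missingness assumption.

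One further analysis is described as a sensitivity analysis: "Sensitivity analyses will then be conducted with SSI total scores from the initial screening and the eligibility interview added to the model". Its stated purpose is to rule out trends that precede treatment.

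Section 3.8 deals with missing data only when setting the sample size ("To account for expected attrition (~25%) and missing data"). The primary analysis is a mixed model with treatment, time and their interaction. H1 is supported if that interaction is statistically significant in favour of CPT+CRP. H2 repeats the analyses in participants with ideation at baseline, so the same rule carries over.

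**The concern.** The decision rule asks the test a question it cannot answer. Little's test compares the observed means across missingness patterns, and its null is MCAR. The plan's ignorable category is MCAR or MAR. A rejection can therefore come from MAR data, and a non-rejection can come from MNAR data. Observed data alone cannot separate MAR from MNAR.

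The response also fails on its own terms. Multiple imputation with no MNAR component assumes MAR, which is the condition just judged not to hold. A likelihood-based mixed model already gives valid inference under MAR if correctly specified. The two branches of the rule therefore rest on essentially the same assumption.

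What is at stake is the branch that nobody examines. Non-response to a suicide-ideation scale could depend on current ideation. If it does, no planned analysis shows how far the conclusion rests on scores that were never seen.

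**Working it through.** **1. The plan's own figures.** With f = d/2 = 0.15, m visits and r = 0.1, the noncentrality is N x m x f^2 / (1 - r).
- N = 112, m = 4: 112 x 4 x 0.0225 / 0.9 = 11.2, with 3 and 330 df, power 0.807 (plan: 80%).
- N = 150, m = 3: 150 x 3 x 0.0225 / 0.9 = 11.25, with 2 and 296 df, power 0.857 (plan: 86%).

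Both reproduce, so the plan's d = 0.3 enters as f = 0.15 for the interaction.

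**2. What f = 0.15 means at week 52.** For arm differences D_t at the four visits, f^2 is the mean of ((D_t - mean D)/2)^2.
- Immediate step (0, D, D, D): f = 0.2165 D, so D = 0.15/0.2165 = 0.69 SD.
- Even divergence (0, D/3, 2D/3, D): f = 0.1863 D, so D = 0.15/0.1863 = 0.80 SD.

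Week-52 biases should be read against 0.69-0.80 SD.

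**3. Simulation settings.** From the documents: 75 per arm, four visits, up to 30% missing follow-up, r = 0.1. Assumed: r = 0.5 as an alternative, normal scores, baseline and week 2 complete, and 30% missing at each of weeks 26 and 52. The log-odds of being missing rise by 0.5 or 1.2 per SD of the driving score. At 0.5, about 20% are missing at -1 SD and 40% at +1 SD; at 1.2, about 9% and 53%.

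**4. Results** (log-odds 0.5 / 1.2). Under MCAR the test rejects in 4-7%.

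| Missingness | r | Little's test rejects | Bias in week-52 contrast |
|---|---|---|---|
| MAR on baseline | 0.1 and 0.5 | 76-79% / 100% | negligible |
| MNAR, same in both arms | 0.1 | 6% / 9% | no false benefit; a true effect is diluted |
| MNAR, same in both arms | 0.5 | 25% / 89% | as above |
| MNAR, one arm only | 0.1 | about 4% | 0.13 / 0.27 SD |
| MNAR, one arm only | 0.5 | 7% / 30% | 0.09 / 0.20 SD |

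Repeated runs agree to about 6 percentage points for rejection rates and 0.02 SD for bias.

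**5. Check on the bias.** Among those observed, the mean of a normal score shifts by b x E[p(1-p)] / (1 - 0.30), where b is the log-odds slope and p the probability of being missing. Numerical integration gives E[p(1-p)] = 0.200 and 0.167. The shifts are 0.5 x 0.200 / 0.70 = 0.14 SD and 1.2 x 0.167 / 0.70 = 0.29 SD. At r = 0.1 the other visits recover almost none of this, in line with the table.

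**6. What a delta analysis could show.** In a linear-time random-intercept model at r = 0.1, the complete-data SE of the 52-week slope difference is 52 x sqrt(2 x 0.9 / (75 x 1784)) = 0.191 SD, where 1784 is the sum of squares of weeks 0, 2, 26 and 52 about their mean. With 30% missing at the last two visits it is about 0.215 SD. An estimate of 0.6 SD has z = 0.6/0.215 = 2.8. It loses significance after a shift of 0.6 - 1.96 x 0.215 = 0.18 SD. At 30% missing in one arm, that is a delta of about 0.18/0.30 = 0.6 SD, holding the SE fixed.

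**The case against.** Several objections have force.

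- **Under MAR the gate does almost no harm.** Either branch is valid if correctly specified. This stands. The practical loss comes from the missing MNAR analysis; the test only gives false reassurance or false alarm.
- **The test is not always silent.** With strong MNAR in both arms and r = 0.5 it rejects in about 89%. This also stands, but rejection only triggers imputation with no MNAR model.
- **Imputation is named.** True, and there is a rule for the number of datasets. What is unspecified is the imputation model and its assumption.
- **One-arm MNAR is unsupported.** Both arms receive the same CPT and differ in safety plan versus CRP. The documents give no reason to expect different dropout mechanisms, so a reader who infers that the trial is biased toward CPT+CRP goes too far. Bias could run either way, and with the same mechanism in both arms there is no false benefit.
- **The simulated data simplify the plan.** They use normal scores, whereas "we expect the primary outcome (suicide ideation) to be positively skewed" and the distributional model is left open. They also treat baseline and week 2 as complete total scores, although the section 4 assessment table lists SSI at Pre-Tx and Tx as EMA only. The sizes are illustrative; the logical error does not depend on them.

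**Conclusion.** The point holds as a matter of definition: the rule cannot identify ignorable missingness, and its remedy assumes what was just rejected. No section supplies an MNAR analysis, with up to 30% of follow-up and 50% of EMA data expected to be missing.

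The size is conditional. Under the assumed one-arm MNAR, the week-52 bias of 0.09 to 0.27 SD is about 11% (0.09/0.80) to 39% (0.27/0.69) of the difference the sample size implies. The effect of MNAR on the EMA estimate was not quantified.

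Two stronger readings are tempting but unsupported. One sets these biases beside 0.3 SD and concludes that they can equal the whole planned effect; section 3.8 uses 0.3 as an interaction effect size, which corresponds to 0.69-0.80 SD at week 52. The other holds that lowering imputed CPT scores cannot matter because SSI has a floor. The plan's criterion is significance, and the 0.18 SD shift in the example lies within the 0.14-0.27 SD that the floor allowed under the assumed skewed score shapes.

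This should be corrected before analysis. It does not invalidate the design or change the sample size.

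**What to change.** 1. Remove Little's test as a gate. State MAR as the primary assumption, with the mixed model fitted by likelihood to all observed data.
2. Whatever any test shows, prespecify an MNAR sensitivity analysis of SSI. Impute using arm, all SSI scores and auxiliaries already collected (screening severity measures, treatment-period EMA), with a method suited to a bounded, skewed score, such as predictive mean matching.
3. Add a delta to the imputed scores, kept within the scale range and varied separately in both arms. Continue until the treatment x time test is no longer significant, which is the plan's own criterion, or the scale limit is reached. Justify the delta range in advance.
4. For EMA, state that MAR is assumed, and repeat the model with a delta on missed prompts that may vary by day. A constant delta with a constant missing rate shifts every day equally and leaves treatment x time unchanged.

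The cost is SAP wording and a little more programming, with no new data. The drawbacks are that the delta range is a judgement to be defended, and that the conclusion may have to be reported as less robust.
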